3.13.3 Vital Signs

Descriptive statistics for vital signs (weight, temperature, blood pressure, pulse rate, and respiratory rate) values and the change from baseline will be presented for each scheduled assessment time point.

3.13.4 ECG

Descriptive statistics for ECG parameters (i.e., PR interval, QRS interval, and QTcF interval) at each time point with triplicate ECGs will be presented for the values and change from baseline scores. (QTcF is the QT interval using Fridericia's correction which is calculated by $QTcF = QT/(RR^{(1/3)})$.)

The number and percentage of subjects with observed QTcF values that satisfy the following conditions will be presented by treatment group and study visit and categorized as: ≤ 450 ms; > 450 to 480 ms; > 480 to 500 ms; and > 500 ms.

The number and percentage of subjects having change from baseline QTcF values that satisfy the following conditions will be presented by treatment group and study visit and categorized as: ≤ 0 ms; > 0 to ≤ 30 ms; > 30 to ≤ 60 ms; and > 60 ms.

3.13.5 Echocardiogram

The results of the echocardiogram (ie, normal, abnormal, and abnormal clinically significant) will be summarized by treatment group for each valve (ie, aortic, mitral, tricuspid, and pulmonic) at each scheduled assessment timepoint.

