- f. Supine 12-Lead ECGs will be performed at Screening, predose, 1, 4, and 8 hours postdose on Days 1 and 14; predose on Days 28 and Months 2 to 12, at each visit on Months 12 to 24; and at the End-of-study visit. Supine ECGs should be repeated 3 times consecutively within 30 minutes (with an interval of at least 1-2 minutes between ECGs). If QTc(F) is prolonged to > 60 msec above baseline at any evaluation or to the level of ≥ 480 msec based on local ECG read, refer to Section 6.7.1.2 for a description of the procedures to be followed.
- g. Clinical laboratory tests will include hematology, serum chemistry, coagulation, TSH, and urinalysis (see Section 7.5.6 for a complete list of assessments). Thyroid stimulating hormone levels will be evaluated at Screening and then every 2 months. Serology testing will be done at Screening only.
- h. Ocular evaluations are to be performed at Screening and at Months 3, 6, 9, 12, 18, and 24, and at the End-of-study visit (if applicable). The following assessments will be performed: evaluation of best corrected visual acuity, fundoscopic exam with non-dilated pupils, slit lamp photography of the iris, non-mydriatic photography of retina within the arcade, and optical coherence tomography of the optic nerve head and macula. Note: if a subject has had ocular evaluations within 3 months of the End-of-study visit, there is no need to repeat ocular evaluations at the End-of-study visit.
- i. Echocardiograms are to be obtained at Screening, on Day 28, at Months 3, 6, 12, 18, and 24, and at the End-of-study visit (if applicable). Echocardiograms should include measurement of ejection fraction and assessment for pericardial effusion and valvular abnormalities. Note: If a subject has had an echocardiogram within 3 months of the End-of-study visit, there is no need to obtain an echocardiogram at the End-of-study visit. If pericardial effusion is diagnosed via echocardiogram, the subject should be rechecked within 1–3 months to monitor for progression.
- j. Pregnancy testing in women of childbearing potential will be performed using urine samples. Subjects must have a negative urine pregnancy test documented within the 24-hour period prior to the first dose of study drug. Pregnancy tests are to be performed at Screening, predose on Day 1, Day 28, Month 3, every 3 months through Month 12, at every visit between Months 12 and 24, and at the End-of-study visit only. Positive urine samples will be confirmed via serum testing.

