4.2. Exclusion Criteria

Subjects meeting any of the following criteria will be excluded from participation.

- 1. Previous partial or total nephrectomy or a kidney transplant.
- 2. Tuberous sclerosis, Hippel-Lindau disease, or acquired cystic disease.
- 3. Congenital absence of 1 kidney and/or need for dialysis or transplantation in the foreseeable future.
- 4. Moderate hematuria. Subjects with microhematuria may be enrolled, unless microhematuria is suspected to be due to infection or recent cyst rupture. If hematuria is due to cyst rupture, the subject may be rescreened after discussion with the Medical Monitor.
- 5. Uncontrolled hypertension (systolic blood pressure > 160 mmHg; diastolic blood pressure > 100 mmHg) while receiving antihypertensive therapy.
- 6. Uncontrolled diabetes mellitus (glycated hemoglobin > 8%).
- 7. Presence of renal or hepatic calculi (stones) causing symptoms.
- 8. Received any investigational therapy within 30 days prior to initiation of therapy (Day 1).
- 9. Received tolvaptan within 30 days prior to initiation of therapy (Day 1).

- 10. Received active treatment (within 4 weeks of initiation of therapy [Day 1]) for urinary tract infection.
- 11. History of pancreatitis or known risk factors for pancreatitis.
- 12. Subject meets any of the following cardiac criteria:
 - Mean QTc interval corrected for heart rate using Fridericia's formula (QTcF) of > 450 msec.
 - History of torsade de pointes, ventricular tachycardia or fibrillation, pathologic sinus bradycardia (< 50 bpm), heart block (excluding first-degree block, being PR interval prolongation only), congenital long QT syndrome or new ST segment elevation or depression or new Q wave on ECG. Inclusion of subjects with a history of atrial arrhythmias should be discussed with the Medical Monitor.
 - Family history of congenital long QT syndrome or unexplained cardiac death.
 - History of ventricular rhythm disturbances.
 - Symptomatic heart failure (per New York Heart Association guidelines), unstable angina, myocardial infarction, or cerebrovascular accident within 6 months prior to study entry.
 - Has a cardiac pacemaker.
 - History of pericardial effusion or presence of pericardial effusion on screening echocardiogram

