If subjects experience an acute onset of new and/or progressive, unexplained pulmonary symptoms such as dyspnea, cough, and fever, study drug should be held while subjects are evaluated. If interstitial lung disease is diagnosed, study drug should be discontinued and treatment administered as necessary.

Hepatotoxicity

Rare cases of hepatic failure have been reported. Confounding factors have included pre-existing liver disease or concomitant hepatotoxic medications. Liver function test abnormalities (including elevated ALT, AST, and bilirubin) have been observed in clinical studies with tesevatinib. Interruption of study drug should be considered in subjects developing liver function abnormality $> 3 \times ULN$.

Management guidelines for liver function abnormalities are provided in Table 5.

Table 5: Management Guidelines for Liver Function Abnormalities

Liver Function Abnormality	Occurrence	Action
Hyperbilirubinemia		
$2.5 - < 3 \times ULN$	1 st	Hold dose; resume dosing when recovered or reduced to mild intensity.
	2 nd	Off study.
> 3 × ULN	1 st	Off study.
AST/ALT elevations		
2.5 – < 3 × ULN	1 st	Hold dose; resume dosing when recovered or reduced to mild intensity.
	2 nd	Hold dose and discuss management with Medical Monitor.
> 3 × ULN	1 st	Hold dose and discuss management with Medical Monitor.
	2 nd	Off study.

Abbreviations: ALT, alanine aminotransferase; AST, aspartate aminotransferase; ULN, upper limit of normal

Pericardial Effusion

Pericardial effusions have been seen in oncology studies with tesevatinib. In addition, 1 subject with ADPKD receiving 50 mg tesevatinib daily developed a trace pericardial effusion. The guidelines outlined below should be followed in the event that a subject develops a pericardial effusion while receiving tesevatinib.

For an asymptomatic pericardial effusion that is at least moderate in size, a follow-up echocardiogram should be performed within 1–3 months to monitor for progression. Results of the additional echocardiogram should be discussed with the Medical Monitor to determine subject management.

Subjects should be monitored for signs and symptoms of cardiac tamponade. In addition to the monthly to bimonthly physical exam of blood pressure, pulse, respiration, weight, heart, and lung, physical exam should also asses for tachycardia, dyspnea, neck vein distension, and edema.

Adrenal Insufficiency

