Electrocardiograms will be performed with the subject in a supine position having rested in this position for at least 5 minutes before each reading. Triplicates should be obtained, with an interval of 1-2 minutes between ECGs.

During the study, all ECGs will be digitally analyzed by a validated central ECG vendor. Additional details on collection of ECGs will be provided in a separate manual.

The QT interval will be corrected using Fridericia's formula, adapted from Fridericia, 1920 12:

$$QT_F = \frac{QT}{RR^{1/3}}$$

All subjects must demonstrate an average screening QTcF value of \leq 450 msec by central digital analysis in order to be enrolled in the study. During the study, immediate clinical management of subjects will be based on results of machine-read ECGs at the sites. However, the central digital analysis will prevail as it becomes available. In addition, the central digital analysis will be used for any AE and SAE documentation.

An increase in QTcF interval (by central digital analysis) to a value > 60 msec above baseline or to the level of ≥ 480 msec requires further monitoring and, after collection of a PK blood sample and discussion with the Medical Monitor on appropriate management, the subject may be removed from the trial (see guidelines in Section 6.7.1.2).

Abnormalities in the ECG that lead to a change in subject management (eg, requirement for additional medication or monitoring) or result in clinical signs and symptoms are considered clinically significant for the purposes of this study and will be recorded on the AE eCRF. If ECG abnormalities meet criteria defining them as serious, they must be reported as an SAE (see Section 8.2.3).

Echocardiogram

Echocardiograms for determination of ejection fraction and evaluation of pericardial effusion and cardiac valve function will be collected at the time points specified in Table 2.

Ocular Monitoring

Ocular monitoring will be performed at the time points specified in Table 2. Ocular monitoring will include an assessment of best corrected distance visual acuity, fundoscopic exam with non-dilated pupils, slit lamp photography of the iris, non-mydriatic photography of retina within the arcade, and optical coherence tomography of the optic nerve head and macula.

Clinical Laboratory Evaluations

A central laboratory will perform clinical laboratory evaluations.

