9.11. Safety Analyses

Safety analyses will be based on the mITT Population.

Treatment-emergent adverse events (TEAE) will be coded using the Medical Dictionary for Regulatory Activities (Version 19.0 or higher). The number of events, incidence, and percentage of TEAEs will be presented by system organ class and by preferred term for each treatment group. Treatment-emergent adverse events will be further summarized by severity and relationship to investigational product. Adverse events related to investigational product, AEs leading to withdrawal, SAEs, and deaths will be summarized/listed.

Clinical laboratory tests (including serum creatinine, cystatin C, and eGFR), vital signs, and ECG findings will be summarized by treatment group and visit. Potentially clinically important findings will also be summarized or listed.

Physical examination, echocardiogram and ocular evaluation findings will be provided in listings.

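### SAP 3.13.5 tabulates echocardiogram results by arm for the four heart valves only; pericardial effusion as read on echo and ejection fraction have no planned by-arm summary

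*SAP*

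**What the plan says.** **What is collected.** Protocol 7.5 (Echocardiogram) gives the test three purposes: "Echocardiograms for determination of ejection fraction and evaluation of pericardial effusion and cardiac valve function will be collected". Footnote i to Protocol Table 2 repeats this as required content: "Echocardiograms should include measurement of ejection fraction and assessment for pericardial effusion and valvular abnormalities". The same footnote sets the timing: "Echocardiograms are to be obtained at Screening, on Day 28, at Months 3, 6, 12, 18, and 24", plus the End-of-study visit if applicable.

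**Why effusion is of interest.** Under Protocol 6.7 (Pericardial Effusion): "Pericardial effusions have been seen in oncology studies with tesevatinib". It adds that "1 subject with ADPKD receiving 50 mg tesevatinib daily developed a trace pericardial effusion", which is the dose studied here. Protocol 4.2 excludes subjects with "History of pericardial effusion or presence of pericardial effusion on screening echocardiogram".

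**What is analysed.** Protocol 9.11 plans no echocardiogram table: "Physical examination, echocardiogram and ocular evaluation findings will be provided in listings". SAP 3.13.5 goes further. Results classed as normal, abnormal or abnormal clinically significant "will be summarized by treatment group for each valve (ie, aortic, mitral, tricuspid, and pulmonic", at each scheduled time point. It has no line for the pericardium or for ejection fraction. SAP 3.13 also keeps results from unscheduled visits out of all safety summary tables.

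**The concern.** The planned table covers one of the three things the echocardiogram is required to assess. Of the other two, effusion is the one the protocol ties to the drug, and it is left to listings and to whatever investigators enter as adverse events.

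Safety and tolerability is a secondary objective, and this trial has a placebo arm. In its background section the protocol says that the lack of a control group in Study KD019-101 made creatine phosphokinase elevations hard to interpret. The same reasoning applies to effusion: a count on tesevatinib means little without the placebo count obtained in the same way. Protocol 9.4 provides for no interim analysis and no data monitoring committee, so the final report is where the arms will be compared. As specified, that report would show valves by arm and effusion by arm only as far as it was reported as an adverse event.

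**Working it through.** The documents state no figure on this point, so there is none to reproduce. The check sets the passages side by side, with short arithmetic for scale.

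**1. Required content against planned by-arm output**

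| Echo content (Protocol 7.5; Table 2 footnote i) | By-arm echo table (SAP 3.13.5) | Other by-arm route |
|---|---|---|
| Valves | Yes, four valves by visit | Adverse event tables, if reported |
| Pericardial effusion | None | Adverse event tables, if reported |
| Ejection fraction | None | None stated for the measurement |

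**2. How complete the adverse event route is for effusion**

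- SAP 3.13.1 tabulates treatment-emergent events by arm, system organ class and preferred term. An effusion entered as an adverse event appears there.
- Protocol 8.1 defines an adverse event broadly enough to include an effusion, and Protocol 4.3 lists symptomatic effusion and tamponade as examples of adverse events leading to discontinuation. Symptomatic cases should be captured.
- For ECG and laboratory results, Protocol 7.5 states explicitly that abnormalities changing subject management go on the adverse event form. No matching sentence exists for echocardiograms.
- For an asymptomatic effusion of at least moderate size, Protocol 6.7 calls for a repeat echocardiogram and discussion with the Medical Monitor. It does not mention an adverse event entry.

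Capture of asymptomatic effusions therefore rests on investigator judgement across 25 to 30 sites. The one ADPKD case cited in the protocol was of trace size, the kind most likely to be handled inconsistently.

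**3. Where rechecks fall.** Footnote i asks for a recheck 1 to 3 months after an effusion is found. Scheduled echocardiograms are 6 months apart from Month 6 to Month 24. A recheck after the Month 6, 12 or 18 study therefore falls between scheduled ones, and the tables would leave it out under SAP 3.13 and the scheduled-time-point wording of SAP 3.13.5.

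**4. Volume.** On-treatment echocardiograms per subject: Day 28 and Months 3, 6, 12, 18 and 24, which is 6. Ceiling: 6 × 100 = 600. For the 80 subjects expected to complete: 6 × 80 = 480. These count scans, not missed effusions.

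**5. What a by-arm effusion table could show with 50 per arm.** The documents give no effusion rate, so the risks below are assumptions.

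- Chance of at least one case on tesevatinib, 1 − (1 − p)^50: 64% at p = 2%, 92% at 5%, 99% at 10%.
- No case in 50: Clopper-Pearson 95% upper limit 1 − 0.025^(1/50) = 7.1% (the SAP's method for binary endpoints, 3.2.1.2).
- Power against an assumed 1% placebo risk, two-sided 0.05, by Φ{[Δ − 1.96·√(2p̄(1−p̄)/n)] / √[p₁(1−p₁)/n + p₂(1−p₂)/n]} with n = 50: about 21% at 5% on tesevatinib, 51% at 10%, 74% at 15%. The normal approximation is rough at these counts.
- Example, 5/50 against 1/50: difference 8%, standard error √(0.10×0.90/50 + 0.02×0.98/50) = 4.7%, Wald 95% CI about −1% to 17%.

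Such a table would describe the data and bound the risk. It would not be a powered test.

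**The case against.** The strongest case against the point is that the SAP breaks no commitment. Protocol 9.11 promises listings only, and the SAP already adds a by-arm table. Valve function is a stated purpose of the test, so that table is legitimate. With about 50 subjects per arm and probably few effusions, a reader could count cases from the listings. The TLF shells are in a separate document (SAP section 4) and might add outputs. Most of this stands, and it limits how much weight the point carries. It does not show that effusion or ejection fraction will be summarised, and hand-counting from listings is a poor substitute for a pre-specified table with a fixed definition and denominator.

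Two stronger readings are tempting, and the documents do not support them.

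- A reader might infer that the drug's known cardiac risk is never compared between arms. That goes too far. Effusions reported as adverse events appear by arm under SAP 3.13.1, and QTcF prolongation, another known cardiac risk, is tabulated by arm, visit and category under SAP 3.13.4.
- A reader might infer that ejection-fraction decline is a known tesevatinib signal left unexamined. The available text does not name it as one. The case for tabulating ejection fraction is only that it is a required measurement with no planned summary.

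It is also not established that effusion size is captured in coded form. Footnote i asks for an assessment of effusion but gives no size categories, and the eCRF is not among the documents.

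**Conclusion.** The point holds in a limited form. SAP 3.13.5 summarises one of three required echocardiogram components by arm. Effusion as read on echo is compared between arms only through adverse event reporting, which is incomplete for asymptomatic findings because no rule requires an entry. Ejection fraction is left to listings.

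Up to 600 scheduled on-treatment echocardiograms are affected. The number of effusions that would go uncounted is unknown. The gap concerns safety reporting under a secondary objective and does not touch the primary analysis. It is still worth closing before unblinding, since effusion is a named tesevatinib finding and the placebo arm allows a like-for-like count.

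This conclusion assumes that the SAP text is the governing specification, that the TLF shells do not already include these tables, and that the eCRF records presence of effusion and the ejection-fraction value as footnote i requires.

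**What to change.** Keep the valve table and extend SAP 3.13.5 with two descriptive by-arm tables in the Safety Population.

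- **(a) Pericardial effusion on echo.** Number and percentage with effusion at each scheduled visit, and number and percentage with any new effusion at any time on treatment. The any-time count should include unscheduled echocardiograms, as a stated exception to the general exclusion in SAP 3.13. Give the risk difference with a 95% CI, preferably by a score or exact method because counts will be small, and the number of subjects with at least one post-baseline echocardiogram as denominator. Add size category where the eCRF captures it. Since effusion at screening is an exclusion, any later effusion is in principle new; entry deviations should be flagged.
- **(b) Ejection fraction.** Value and change from baseline by visit.

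State that both tables are descriptive and that no hypothesis test is planned.

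The cost is two extra tables from assessments the protocol already requires, plus a check of how the eCRF records effusion size. No change to the visit schedule, subject management or the primary analysis is needed.

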3.13.2 Clinical Laboratory Evaluation

The summary statistics (including number, mean, standard deviation, median, minimum, and maximum) of all laboratory variables and changes from baseline will be calculated for each visit or study assessment by treatment group. For parameters of white blood cell counts, neutrophils (absolute count), lymphocytes (absolute count),

monocytes (absolute count), hemoglobin, platelets, ALP, ALT, aspartate aminotransaminase, gamma glutamyl transferase, total bilirubin, glomerular filtration rate, plots of mean/mean changes from baseline with the corresponding standard error will be displayed.

For shift tables, laboratory results will be classified using the common terminology criteria for adverse events (CTCAE) Version 5.0. All graded laboratory parameters will be summarized separately for hematology and biochemistry. Corresponding shift tables comparing baseline to the worst post-baseline grade within the treatment period will be provided.

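### The planned valve table counts findings at each visit but does not compare each subject with their own screening echocardiogram, so new or worsened findings are not tabulated

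*SAP*

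**What the plan says.** SAP 3.13.5 grades each valve as normal, abnormal, or abnormal and clinically significant. It states that these results "will be summarized by treatment group for each valve (ie, aortic, mitral, tricuspid, and pulmonic) at each scheduled assessment timepoint". It mentions no change from baseline, no shift, and no new-or-worsened category.

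The screening comparator exists. Protocol Table 2, footnote i, states: "Echocardiograms are to be obtained at Screening, on Day 28, at Months 3, 6, 12, 18, and 24, and at the End-of-study visit" (the last of these where applicable). The same footnote sets the content: "Echocardiograms should include measurement of ejection fraction and assessment for pericardial effusion and valvular abnormalities".

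The only echocardiographic bar to entry is in Protocol 4.2, criterion 12: "History of pericardial effusion or presence of pericardial effusion on screening echocardiogram". No criterion names valve abnormality.

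Protocol 9.11 promises less than the SAP: "Physical examination, echocardiogram and ocular evaluation findings will be provided in listings".

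The neighbouring SAP sections do compare with baseline. For laboratory data (3.13.2): "Corresponding shift tables comparing baseline to the worst post-baseline grade within the treatment period will be provided". For ECG (3.13.4), QTcF is also categorized by change: "The number and percentage of subjects having change from baseline QTcF values that satisfy the following conditions". Vital signs (3.13.3) are summarized both as values and as change from baseline.

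**The concern.** The useful question for valve data is whether a subject's valves become abnormal, or more abnormal, after starting study drug, and whether this happens more often on tesevatinib than on placebo. A count of abnormal results at a visit answers something else: how many of the subjects examined that day have an abnormal valve, whenever it arose.

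Because pre-existing valve findings are allowed at entry, the two can differ widely. A count can stay flat while new cases replace resolved ones. It can fall because affected subjects have left. At stake is a descriptive safety signal that the collected data could show and the planned table may not.

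**Working it through.** **1. Is there any within-subject comparison for valves?** Setting the SAP safety sections side by side:

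| Data | Within-subject comparison in the SAP |
|---|---|
| Laboratory (3.13.2) | Change from baseline; shift from baseline to worst post-baseline grade |
| Vital signs (3.13.3) | Change from baseline |
| ECG (3.13.4) | Change from baseline; QTcF change categories |
| Echocardiogram, valves (3.13.5) | None stated |

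**2. Is a baseline available?** Yes. SAP 3.2.3 takes the last valid value within 28 days before first dose. The protocol synopsis extends screening to 42 days only for MRI and ocular assessments, so a screening echocardiogram done on schedule qualifies.

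**3. What do visit counts reveal about new cases?** Let *n* be the subjects seen at both times, *s* the number abnormal at screening and *m* the number abnormal at the later visit. New cases must lie between max(0, *m* − *s*) and min(*m*, *n* − *s*). Take *n* = 50 (the planned arm size, with everyone still attending). The counts are illustrative, because the documents give no screening prevalence.

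- *s* = 15, *m* = 15: lower limit max(0, 0) = 0; upper limit min(15, 35) = 15. New cases: **0 to 15**.
- *s* = 15, *m* = 18: lower limit max(0, 3) = 3; upper limit min(18, 35) = 18. New cases: **3 to 18**.

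**4. What does attrition add?** The protocol synopsis anticipates at least 40 of 50 completers per group. Suppose 15 of 50 (30%) are abnormal at screening, 10 subjects leave, and 8 of the leavers were among the 15. Then 7 abnormal subjects remain. If 3 others become abnormal, the later count is 10 of 40 (25%): the percentage falls although three new abnormalities appeared. The split of leavers is an assumption chosen to show the mechanism.

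**5. Does it change the chance of seeing a difference between arms?** This is illustration only, since the SAP plans no test on echocardiogram results. Assume 45 evaluable subjects per arm, new onset of 2% on placebo, screening abnormalities that persist, and no dropout. With screening prevalence *b* and new-onset rate *i*:

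- visit prevalence is *b* + (1 − *b*) × *i*, compared on 45 per arm;
- new onset is *i*, compared on 45 × (1 − *b*) per arm, which is 36 at *b* = 20% and 27 at *b* = 40%.

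For example, at *b* = 20% and *i* = 20%, visit prevalence is 0.20 + 0.80 × 0.20 = 36.0%, against 0.20 + 0.80 × 0.02 = 21.6% on placebo. The chance of p < 0.05 by Fisher's exact test, by full enumeration, is:

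| New onset, tesevatinib vs placebo | *b* = 20%: prevalence / new onset | *b* = 40%: prevalence / new onset |
|---|---|---|
| 10% vs 2% | 6.7% / 8.0% | 4.5% / 2.9% |
| 20% vs 2% | 25% / 56% | 12% / 32% |
| 25% vs 2% | 39% / 78% | 18% / 54% |

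The gain is substantial at 20% or more against 2%. At about 10% against 2% there is essentially none.

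**The case against.** Much of the case on the other side stands.

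- **Screening is a scheduled timepoint.** A reader might infer that the SAP allows no comparison with screening at all. The documents do not support that. Read with Table 2, the by-visit table will probably show the screening distribution by arm and valve. Only the within-subject link is missing, but step 3 shows that having both counts does not supply it.
- **The information is kept elsewhere.** Protocol 9.3 and 9.11 provide listings. Protocol 8.1.1 requires worsening of a pre-treatment event to be recorded as a new adverse event, and SAP 3.13.1 counts events that occur or worsen after first dose. Clinically significant new or worsened valve findings should therefore be tabulated by arm as adverse events. Findings not recorded as adverse events appear only in listings, where a reader would have to build the arm comparison by hand.
- **Randomization balances pre-existing findings on average.** This is correct. A reader might infer a biased comparison, but old findings add to both arms alike. They dilute a difference; they do not create one.
- **No valve-specific signal is described.** Protocol 6.7 covers pericardial effusion but lists no valve toxicity. This limits the priority, although the sponsor chose to collect and tabulate valve results.
- **The SAP already exceeds the protocol's listings, and the table shells are in a separate document not available here.** The shells may contain a shift table. The SAP text still does not call for one, as it does for laboratory grades.

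**Conclusion.** The gap is real but small. As written, SAP 3.13.5 gives visit-by-visit counts from which the number of new or worsened valve findings cannot be recovered. With 15 of 50 abnormal at both times, the data fit anything from 0 to 15 new cases. The practical loss is mainly new or worsened findings that were not recorded as adverse events.

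A reader might take the larger differences in the illustrative power table as the size of the problem. They should not carry that weight: the new-onset rates and screening prevalences are not in the documents, no test is planned, and the advantage vanishes at about 10% against 2%. The conclusion rests instead on the wording of 3.13.5, on the lack of a valve exclusion, and on the fact that two marginal counts do not identify new cases. It is a worthwhile improvement that does not affect the trial's validity.

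**What to change.** In SAP 3.13.5, keep the by-visit table and add, by arm:

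- for each valve, a shift table from the screening result to the worst post-baseline result;
- the number and percentage of subjects with any new or worsened valve finding.

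Name the screening echocardiogram as baseline. Use as denominator the subjects with a screening result and at least one later result, and state whether End-of-study and unscheduled echocardiograms count towards the worst result. This follows the SAP's existing approach to laboratory grades. A worst-result table retains findings from subjects who leave later, but it still depends on how long each subject was followed, so the denominators and exposure by arm should be read alongside it.

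The cost is one extra descriptive table from data already collected, plus a few lines of SAP text. No visit, procedure or clinical rule changes.
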